13.5 Statistical Analysis for Exploratory Objectives

The study is not sufficiently powered to establish definitive outcomes for the correlative exploratory endpoint. Any comparison with a significant alpha, 0.05, will be deemed of interest to warrant further evaluation. An ordinal regression and a logistic regression will be used to assess the association between expression of each biomarker and clinical response.

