1.2.1 Pazopanib in RCC

In RCC, systemic treatment for many patients who have metastatic disease involves drugs targeting angiogenesis. High-dose interleukin 2 in the front-line setting is still recommended for patients with Karnofsky performance status of > 80%, and other immune-based therapies with immune checkpoint inhibitors are showing promise. However, agents targeting angiogenesis remain a cornerstone in the management of this disease. Two different approaches have demonstrated clinical activity in blocking the VEGF pathway. Clinical anticancer activity has been observed with small molecule tyrosine kinase inhibitors (TKIs) (eg, pazopanib, sunitinib, sorafenib, and axitinib) which block the intracellular domain of the VEGF receptor, as well as the monoclonal antibody bevacizumab which can bind circulating VEGF and prevent activation of the VEGF receptor. Among the TKIs, pazopanib and sunitinib are accepted first-line treatment options ($\underline{7}$).

In a randomized phase 3 study of pazopanib versus sunitinib in 1,110 previously untreated patients with advanced RCC, partial responses were observed in 170 patients in the pazopanib group (31%), and one patient had a complete response ($\underline{7}$). The median progression-free survival was 8.4 months with pazopanib (95% confidence interval [CI], 8.3 to 10.9), and the median duration of treatment was 8.0 months (range, 0 to 40) in the pazopanib group. Regarding tolerability, 44% of patients treated with pazopanib had a dose interruption of 7 days or more and 44% of patients had a reduction in the dose. The proportion of patients who discontinued the study drug because of adverse events was 24%. These data demonstrate a favorable pazopanib safety profile compared to sunitinib, with similar efficacy. The results of this study established pazopanib as an acceptable front-line choice in the treatment of RCC with TKI-based therapy.

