1.2.2 Pazopanib in STS

The interaction between VEGF and its receptors involved in angiogenesis plays a role in STS tumor progression and prognosis ($\underline{8}$). Two studies found that high VEGF serum levels correlated strongly with the most poorly differentiated STS ($\underline{9}$, $\underline{10}$).

The randomized multicenter phase 3 "PALETTE" study evaluated pazopanib compared to placebo in 369 patients with STS that had progressed following front-line therapy (11). In this study, the best overall response for patients taking pazopanib was a partial response in 14 of 246 (6%), stable disease in 164 (67%), and progressive disease in 57 (23%). Median progression-free survival was 4.6 months (95% CI 3.7-4.8) for pazopanib compared to 1.6 months (95% CI 0.9-1.8) for patients who received placebo, and median overall survival was 12.5 months (10.6-14.8) compared to 10.7 months (8.7-12.8) for the placebo arm.

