1.5 Rationale for the Study

Most highly active cancer chemotherapy regimens involve multiple agents. Pazopanib is an FDA-approved agent for the treatment of both advanced RCC and STS. AR-42 is a broad-spectrum inhibitor of HDAC and non-histone protein deacetylation (pan-DAC inhibitor) which has also been shown to inhibit Akt by a deacetylation-independent mechanism. Preclinical studies in both tumor cell lines and animal tumor models have shown promising anticancer effects of the combination of AR-42 and pazopanib suggesting that the combination should be tested clinically. Preclinical studies also suggest that these promising anticancer effects may be related to modulation of tumor cell autophagy. This phase 1 study will identify recommended phase 2 doses (RP2Ds) of AR-42 and pazopanib when given in combination for subsequent clinical trials and may potentially identify candidate pharmacodynamic and predictive biomarkers.

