3.4 Exploratory Endpoint

Expression of CD95 and other proteins of interest by immunohistochemical (IHC) analysis using archived tumor samples from the most recent diagnostic biopsy or surgery (performed before initiation of study treatment) correlated with response to study treatment

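### Section 13.5 tests each biomarker against response across pooled RCC and STS with no tumor-type term, so a protein that merely tracks tumor type can pass the 0.05 screen

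*Combined protocol and SAP*

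**What the plan says.** Section 13.5 (Statistical Analysis for Exploratory Objectives) gives the model: "An ordinal regression and a logistic regression will be used to assess the association between expression of each biomarker and clinical response". It gives the screening rule: "Any comparison with a significant alpha, 0.05, will be deemed of interest to warrant further evaluation". It also carries a disclaimer: "The study is not sufficiently powered to establish definitive outcomes for the correlative exploratory endpoint". No covariate or stratum is named.

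Section 4.1.1 admits RCC and STS of any histologic type, and Section 13 provides no separate biomarker analysis for the two diseases. Section 3.4 fixes the specimen and the comparison: "archived tumor samples from the most recent diagnostic biopsy or surgery (performed before initiation of study treatment) correlated with response to study treatment". Sections 11.1 and 11.3 and Tables 19 and 20 add no on-treatment sample. Section 3.1 describes a single arm, with both drugs given to everyone.

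The background gives pazopanib response rates for both diseases: 31% partial response in previously untreated advanced RCC (Section 1.2.1), and 14 of 246, or 6%, in STS that had progressed after front-line therapy (Section 1.2.2). Section 1.5 says that the study "may potentially identify candidate pharmacodynamic and predictive biomarkers".

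**The concern.** On the documents' figures, tumor type is strongly related to response. Expression of a protein on immunohistochemistry may also differ between a carcinoma and a sarcoma. A factor related to both marker and outcome confounds their association. A marker-by-marker regression over the pooled patients would then give part of the RCC-versus-STS difference to the marker.

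What is at stake is the list of proteins taken forward. Under the 0.05 rule as written, a protein that separates RCC from STS could be flagged as related to response to the combination. More patients do not cure this, because the error is bias and grows easier to detect as enrolment rises. The RP2D, the safety analysis and the response-rate estimate are not touched.

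**Working it through.** **Sample size available.** Section 13.5 gives no number of its own, so the trial total applies. Section 13.2 reproduces:
- Maximum: 36/0.8 = 45; 45 + 6 = 51.
- Lower likely figure: 4 × 4.5 = 18; 18/0.8 = 22.5, rounded up to 23; 23 + 6 = 29.
- Upper likely figure: 5 × 4.5 = 22.5, rounded up to 23; 23/0.8 = 28.75, rounded up to 29; 29 + 6 = 35.

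**Strength of tumor type.** Odds ratio for response, RCC versus STS: (0.31/0.69) / (14/232) = 0.449/0.0603 = 7.4.

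**Expected responders.** N × [s × 0.31 + (1 − s) × 14/246], where s is the RCC share. The documents do not state s; 30% to 70% is assumed.
- N = 29: 3.9 (s = 0.3) to 6.8 (s = 0.7)
- N = 35: 4.6 to 8.2
- N = 51: 6.8 to 11.9

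So about 4 to 12 responders are expected, or fewer where tissue is not available.

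**Pooled odds ratio when the marker has no effect within either tumor.** Assume an equal mix, response of 31% and 6%, and a marker high in a fraction a of RCC and 1 − a of STS. Then the response rate is 0.31a + 0.06(1 − a) if the marker is high, and 0.31(1 − a) + 0.06a if it is low.

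| High in RCC / STS | Response, high | Response, low | Pooled odds ratio | Within-tumor odds ratio |
|---|---|---|---|---|
| 70% / 30% | 0.235 | 0.135 | 1.97 | 1.0 |
| 80% / 20% | 0.260 | 0.110 | 2.84 | 1.0 |
| 90% / 10% | 0.285 | 0.085 | 4.29 | 1.0 |

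With 14/246 in place of the rounded 6%, these are 2.00, 2.91 and 4.44.

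**False-hit rate.** Simulation with 20,000 trials per setting, two-sided 0.05 (the plan gives no sidedness), response 31% in RCC and 14/246 in STS, and no within-tumor effect. N = 35, about half RCC:

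| High in RCC / STS | Unadjusted logistic (likelihood ratio) | Unadjusted Fisher exact | Mantel-Haenszel, stratified by tumor type |
|---|---|---|---|
| 50% / 50% | 6.8% | 2.7% | 4.8% |
| 70% / 30% | 14.6% | 7.3% | 4.5% |
| 80% / 20% | 25.4% | 14.6% | 4.7% |
| 90% / 10% | 39.5% | 25.8% | 4.6% |

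The first row has no confounding, and the unadjusted logistic test already rejects 6.8% there because the sample is small. The excess due to tumor type is therefore 14.6 − 6.8 = 7.8 points at 70/30, 18.6 at 80/20 and 32.7 at 90/10.

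- **Sample size.** At 80/20 the unadjusted logistic rate is 23.3% at N = 29, 25.4% at N = 35 and 31.2% at N = 51.
- **Tumor mix.** At N = 35 with 30% RCC the rates are 14.7% (70/30) and 37.6% (90/10). With 70% RCC they are 12.0% and 32.7%.
- **Continuous marker.** At N = 35 (3,000 trials), with the RCC mean higher by 1, 1.5 or 2 SD, the unadjusted rates are 14.9%, 22.1% and 28.7%. With tumor type in the logistic model they are 6.6%, 7.1% and 6.9%.

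The ordinal model was not simulated.

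**Sparse STS responders.** With 15 STS patients at 6%, the chance of no STS responder is 0.94^15 = 0.395, about 40%. Ordinary maximum likelihood then has no finite tumor-type coefficient.

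**The case against.** The strongest reply has five parts.

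1. **The analysis is exploratory and says so.** Section 13.5 disclaims definitive outcomes and treats a hit only as a reason to look further. That stands, and it limits how much the point matters. But low power concerns imprecision and missed effects. It does not cover a bias that creates hits.

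2. **Adjustment is not ruled out.** Both regressions accept covariates, and the text does not say that they will be univariable. That stands: the fault is under-specification. Left open, however, the choice would fall after the data are seen.

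3. **The size rests on assumptions.** The documents report no protein expression by tumor type, no RCC:STS mix and no response rates for the combination. The 31% and 6% come from untreated RCC and pretreated STS, whereas this trial excludes prior pazopanib but does not otherwise restrict RCC to untreated patients. The gap in this trial could be smaller. All of this stands.

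4. **Adjustment is not free.** With few responders, and possibly none in STS, ordinary adjusted regression may fail. RCC/STS is also a coarse split when Section 1.1.2 counts more than 50 STS entities. Both stand and shape the fix.

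5. **The biomarker wording in Section 1.5 is hedged.** A reader might infer that the protocol promises pharmacodynamic and predictive markers, or that archived tissue makes the correlative study worthless. The documents support neither reading. Section 1.5 speaks only of possible candidates, and the objective (2.3) and endpoint (3.4) only correlate expression with response. Pre-treatment tissue is a suitable specimen for a baseline marker. It cannot show a drug-induced change, and without a control arm a predictive marker cannot be told from a prognostic one, nor AR-42 from pazopanib. That affects one background sentence and no result.

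**Conclusion.** The point holds as a gap in specification with a cheap remedy. Section 13.5 fixes a model and a screening rule but leaves out a baseline factor that, on the documents' figures, carries an odds ratio for response of about 7.4. If a marker is high in 70% to 90% of RCC and 30% to 10% of STS, the pooled odds ratio is about 2.0 to 4.3 with no within-tumor relation. The false-hit rate at N = 35 is then roughly 15% to 40%, against about 5% when stratified.

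These figures assume that degree of imbalance, a roughly equal mix, and response rates on the combination equal to those quoted for pazopanib alone. A reader might infer that any hit would merely identify RCC. The documents do not support that: nothing in them says how CD95 or any other protein is distributed between the two tumors, and a balanced marker is not confounded by tumor type.

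**What to change.** In Section 13.5, make the analysis stratified by or adjusted for tumor type (RCC/STS) the sole basis for calling a marker of interest, and report the unadjusted result beside it. Name the method in advance and choose one that tolerates sparse responders: an exact or stratified test for a binary marker, a stratified rank test or penalized logistic regression for graded or continuous expression, and tumor type as a stratum or term in the ordinal analysis. State that if no STS patient responds, the binary analysis rests on RCC alone and will be reported as such.

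As a minor wording change in Section 1.5, describe the markers as candidate baseline markers associated with response.

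The cost is a few sentences, with no new samples, visits or patients, since tumor type is known at entry. The price in the analysis is some loss of precision, a fair chance (about 40% with 15 STS patients at 6%) that STS contributes nothing to the binary analysis, and remaining heterogeneity within STS that a two-level factor cannot remove.

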13.2 Sample Size/Accrual Rates

With the 7 proposed dose levels (-1, 1, 2, 3A, 3B, 4A, and 4B) and starting at dose level 1 (as indicated in Table 1 in Section 6.6), the number of patients needed for evaluation of DLT ranges from 4 to 36. To take into account the up to 20% of patients subsequently found to be inevaluable for DLT, the maximum number of patients required to determine the MTD is 45. Per the dose-escalation plan, it is likely that 4-5 dose levels will be explored. With an average of 4.5 patients per cohort, the likely scenarios involve 18-23 patients and, therefore, it is expected that 23-29 patients evaluable for DLT will be enrolled in the study. With 6 additional patients who will be treated at the MTD, the maximum number of patients needed for the study is 51 with a likely sample size of 29-35 patients.

Based on past recruitments, the recruitment rate is expected to be about 1-2 per month. Therefore, the anticipated enrollment period is expected to be about 15-35 months.

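### The biomarker screen names no test type or small-sample method; with about 4–6 plausible responders, default Wald p-values can reject a marker because it separates responders well

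*Combined protocol and SAP*

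**What the plan says.** Section 13.5 gives the whole method for the exploratory endpoint: "An ordinal regression and a logistic regression will be used to assess the association between expression of each biomarker and clinical response". The decision rule is "Any comparison with a significant alpha, 0.05, will be deemed of interest to warrant further evaluation". The section also concedes that "The study is not sufficiently powered to establish definitive outcomes for the correlative exploratory endpoint".

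It does not say whether p-values come from a Wald, likelihood-ratio or score test. It does not mention penalised or exact estimation, or what happens if a fit diverges. No other part of section 13 supplies this.

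Section 13.2 sets the size: "the maximum number of patients needed for the study is 51 with a likely sample size of 29-35 patients". Section 13.6.3 counts PR or CR as response and everything else as non-response. Sections 11.1 and 11.3.1 make tissue collection conditional on availability. Section 11.3 specifies immunohistochemistry but gives no scoring scale or positivity cut-off.

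**The concern.** A logistic model with one marker has no finite maximum-likelihood solution when responders and non-responders are separated by the marker. For a yes/no marker, one empty cell is enough, such as no responder among the marker-negative patients. The software then stops at an arbitrary large coefficient with a far larger standard error, and the ratio of the two gives a Wald p-value near 1.

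An empty cell is most likely when the marker is strong and responders are few. A screen that reads the default coefficient p-value can therefore lose detection as the true signal grows, which low power alone does not do. The exploratory objective is to relate CD95 and other proteins to response, and section 1.5 presents candidate predictive biomarkers as a possible product of the trial. A good candidate could be set aside for a numerical reason. If the test is instead chosen after the data are seen, the same table can be called of interest or not depending on that choice.

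**Working it through.** **1. The plan's own sample size reproduces.** Dividing by 0.8 for the 20% inevaluable and adding 6 patients at the MTD:
- maximum: 36/0.8 = 45; 45 + 6 = 51
- likely: 18/0.8 = 22.5, rounded to 23, and 23/0.8 = 28.75, rounded to 29; adding 6 gives 29–35

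**2. Expected responders.** The rates are from sections 1.2.1 (31%, RCC) and 1.2.2 (6%, STS), both for pazopanib alone. The RCC share f is not in the documents. Expected responders = N × [0.31f + 0.06(1 − f)].
- f = 0.5 (assumed): rate 18.5%; 29 × 0.185 = 5.4 and 35 × 0.185 = 6.5
- the same with tissue in 80% (assumed): 4.3 to 5.2
- extremes: 29 × 0.06 = 1.7 (all STS) and 35 × 0.31 = 10.8 (all RCC)

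**3. One table, four tests.** Take 24 patients, 12 marker-positive, with 5 responders who are all positive.
- Fisher: 2 × C(12,5)/C(24,5) = 1584/42504 = 0.037
- likelihood-ratio: 0.004
- Firth penalised likelihood-ratio: 0.013
- Wald from the ordinary fit: coefficient 25.9, standard error 85733, p = 0.9998 (the first two depend on when the iterations stop; p stays near 1)

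**4. The ranking inverts.** With 5 responders and 25 non-responders:

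| Positive responders | Positive non-responders | Wald | LR | Fisher | Firth |
|---|---|---|---|---|---|
| 4/5 | 5/25 | 0.024 | 0.010 | 0.019 | 0.013 |
| 5/5 | 5/25 | 0.998 | 0.0003 | 0.0018 | 0.0010 |
| 5/5 | 10/25 | 0.997 | 0.005 | 0.042 | 0.016 |
| 5/5 | 13/25 | 0.997 | 0.016 | 0.066 | 0.052 |

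**5. How often separation occurs.** The chance that all 5 responders are positive is s⁵, where s is true positivity in responders: 0.8⁵ = 33%, 0.9⁵ = 59%, 0.95⁵ = 77%. With 30% of non-responders positive, exact enumeration gives:

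| s | Wald detection | Fisher detection |
|---|---|---|
| 80% | 15% | 53% |
| 90% | 11% | 74% |
| 95% | 7% | 84% |

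In a milder case, response is 30% in marker-positive and 6% in marker-negative patients, with equal groups. The chance of no responder among the negatives is 0.94¹² = 48% (n = 24) or 0.94¹⁵ = 40% (n = 30). Wald power is about 5–6%, against 29–39% for Firth.

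**6. Continuous marker, 5 against 25 patients (2000 simulated trials).** Wald detection is 39% at a shift of 1 SD, about 68% at 2 SD, 27% at 3 SD and 3% at 4 SD. The likelihood-ratio and Mann-Whitney tests are near 100% at 3 and 4 SD. The reversal therefore needs a very strong marker.

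**7. The planned ordinal model (PD < SD < response).** With all 5 responders positive, 15 SD and 10 PD, Wald p depends on how the other positives fall:

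| SD positive | PD positive | Wald p |
|---|---|---|
| 6/15 | 2/10 | 0.011 |
| 7/15 | 3/10 | 0.025 |
| 5/15 | 3/10 | 0.038 |
| 6/15 | 4/10 | 0.086 |
| 4/15 | 6/10 | 0.56 |
| 0/15 | 0/10 (perfect marker) | 0.99 |

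**8. False positives at nominal 0.05.** The plain likelihood-ratio test rejects about 7–9% of null markers, Firth about 4%, and Fisher about 1–3%.

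**The case against.** Section 13.5 does not say Wald. A likelihood-ratio, score, exact or Firth p-value for the same logistic model would usually flag these markers. This stands, so the conclusion is conditional. It does not close the gap: Wald is the usual coefficient p-value, and the plain likelihood-ratio test carries its own excess of false positives.

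The plan also fits an ordinal regression, and either model can trigger interest. This stands in part. For the 24-patient table in step 3, the ordinal Wald p-value is 0.024 with 14 SD and 5 PD (one PD positive), and 0.017 or 0.044 with 13 SD and 6 PD (one or two positive). Other splits give 0.066 and 0.14.

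A reader might infer that the screen is bound to miss the best marker, or that its power is zero. The documents do not support that. No test is named, the ordinal model sometimes succeeds, and no yes/no cut-off is specified. Zero power arises only in a scenario such as 36% against 0% response, which forces an empty cell in every dataset. On a continuous score, Wald detection keeps rising up to roughly a 2 SD shift.

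Finally, the analysis is exploratory and admits low power, and no dose or safety decision rests on it. That limits the consequence. It does not justify a test whose detection can fall as the signal strengthens.

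**Conclusion.** The concern holds as a conditional one. Section 13.5 leaves the p-value undefined at responder counts where the choice decides the result: the same 24-patient table gives 0.004, 0.013, 0.037 or about 1. If default Wald p-values are used, logistic detection of a dichotomised marker falls from 15% to 7% as positivity in responders rises from 80% to 95%, while Fisher rises from 53% to 84%. The ordinal model is a partial safeguard only.

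This rests on assumptions that the documents do not settle: an equal RCC/STS mix, response rates like those of pazopanib alone, tissue in 80–100% of patients, two-sided testing and, for the main figures, a dichotomised marker. An STS-heavy mix makes separation more likely and an RCC-heavy mix less so. It is a worthwhile improvement to an exploratory analysis and does not threaten the trial's primary objective.

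**What to change.** In section 13.5:
- For response against non-response, specify Firth-penalised logistic regression with penalised likelihood-ratio p-values, or exact logistic regression.
- For ordinal response, specify a penalised proportional-odds model or an exact trend or rank test.
- State that Wald p-values will not be used, and apply the 0.05 screen only to the p-values named above.
- Treat Fisher's exact test as optional for dichotomised markers, because it is conservative.

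The cost is a few sentences of SAP text and slightly less familiar software output. No extra patients, samples or data are needed. The change does not cure the low power: Firth reaches only 29–39% in the 30% against 6% case, so results remain hypothesis-generating.

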13.6 Evaluability for DLT, Toxicity, and Response

13.6.1 DLT-Evaluable Population

DLT-evaluable patients are those who have taken a minimum of 6 doses of AR-42 during the first treatment cycle and a minimum of 21 doses of pazopanib during the first treatment cycle, or those who have experienced a DLT with any study treatment during cycle 1 as described in Section 6.7.1.

Note: Patients who for any reason are not evaluable for DLT will be replaced.

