6.2 Administration of Study Treatment

- 6.2.1 AR-42 Administration and Treatment Schedule
 - AR-42 tablets will be taken orally once per day on 3 non-consecutive days per week (eg, Monday, Wednesday, and Friday) during the first 3 weeks of each 4-week cycle (ie, a total of 9 doses). A 7-day "AR-42 rest period" during which AR-42 will not be taken is required at the end of each cycle (ie, AR-42 will not be taken by the patient during week 4 of each 4-week cycle).
 - If treatment must be interrupted during the cycle, the cycle may be extended to a maximum of 5 weeks. If the cycle has been extended to 5 weeks, all doses of AR-42 (ie, a total of 9 doses) must be taken during the first 4 weeks of the extended cycle (ie, if the cycle was extended, AR-42 will not be taken by the patient during week 5 of the 5-week cycle).
 - Patients will be instructed as follows:
 - Take AR-42 once per day on 3 non-consecutive days during the first 3 weeks of each 4-week cycle.
 - Take AR-42 tablets with water on an empty stomach, ideally the first thing in the morning at least 1 hour before breakfast. If necessary, doses can be taken at least 1 hour before or at least 2 hours following any meal.
 - Swallow the AR-42 tablets whole.
- 6.2.2 Pazopanib Administration and Treatment Schedule
 - Pazopanib tablets will be taken orally once daily continuously during each treatment cycle. There are no scheduled breaks in pazopanib therapy.
 - Patients will be instructed as follows:
 - Take pazopanib once daily during each 4-week cycle
 - Take pazopanib tablets with water on an empty stomach, ideally the first thing in the morning at least 1 hour before breakfast. If necessary, doses can be taken at least 1 hour before or at least 2 hours following any meal.
 - Swallow the pazopanib tablets whole.

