6.7 Definitions of Dose-Limiting Toxicity, Maximum Tolerated Dose, and Recommended Phase 2 Dose

6.7.1 DLT-Evaluable Criteria

The DLT evaluation period will be the first treatment cycle. Patients must have taken a minimum of 6 AR-42 doses **and** a minimum of 21 pazopanib doses during cycle 1 to be considered evaluable for DLT, if DLT has not been observed at the delivered dose.

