6.7.3 MTD

Dose escalation will follow a modified 3+3 plan (Table 3) using the dose levels listed in Table 1 and the guidelines in Table 2 to determine the MTDs and the RP2Ds for AR-42 and pazopanib. DLT is defined in Section 6.7.2. Patients will be enrolled in cohorts of 3 beginning at dose level 1.

Table 3. Modified 3+3 Dose Escalation		
Number of Patients with DLT at a Given Dose Level (Refer to Section 6.7.2 for DLT definition)	Escalation Decision Rule (Refer to Table 1 in Section 6.6 for dose levels and Table 2 for dose-escalation guidelines)	
0 out of 3	Enroll 3 patients at the next dose level.	
≥ 2 ^A	MTD has been exceeded. No further treatment at this dose is allowed. Three (3) additional patients will be enrolled per dose levels as noted on Table 2 .	
1 out of 3 ^A	Enroll at least 3 more patients at this dose level.	
	 If 0 of these 3 patients experience DLT, escalate doses to the next dose level (unless MTD has already been exceeded at that dose level, in which case, the current dose level is the MTD).^B 	
	• If 1 or more of this group experience DLT (total of 2), then the MTD has been exceeded. Three (3) additional patients will be enrolled at the next lower dose level if only 3 patients were treated previously at that dose. ^B	
Patients enrolled to complete a total enrollment of 12 at the MTD		
≤ 3	The MTD has been confirmed. ^B	
≥ 4	The MTD has been exceeded; 3 additional patients will be enrolled at the next lower dose level (if available). ^B	
	3 PPE at any dose level will NOT be considered a DLT. grade 3 PPE will be considered DLT.)	
 B. Confirmation that a dose level does not exceed the MTD requires evaluation of a minimum of 6 DLT-evaluable patients. To confirm the RP2Ds, additional patients will be enrolled at the MTDs until a total of 12 patients have been treated at the MTDs. 		

 Table 3. Modified 3+3 Dose Escalation

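### DLT-evaluability is a dose count that can be met on day 21 of a 28- to 35-day DLT period, so a patient who leaves after that counts as DLT-free, and the enrolment period allows no time for cohorts to finish cycle 1

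*Combined protocol and SAP*

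**What the plan says.** - **DLT window.** Section 6.7.1: "The DLT evaluation period will be the first treatment cycle". A cycle is 4 weeks, and Section 6.2.1 adds: "If treatment must be interrupted during the cycle, the cycle may be extended to a maximum of 5 weeks". The window is therefore 28 days, or up to 35.
- **Evaluability without a DLT.** Section 13.6.1: "DLT-evaluable patients are those who have taken a minimum of 6 doses of AR-42 during the first treatment cycle". Section 6.7.1 gives the pazopanib part: "a minimum of 21 pazopanib doses during cycle 1 to be considered evaluable for DLT, if DLT has not been observed at the delivered dose". Neither section adds a length of observation. Only patients who are not evaluable are replaced.
- **Dosing.** Section 6.2.2: "Pazopanib tablets will be taken orally once daily continuously during each treatment cycle". AR-42 is taken on 3 non-consecutive days a week for 3 weeks, 9 doses in all.
- **Follow-up after stopping.** Section 6.13 keeps patients under observation for 30 days after the last dose, except those who withdraw consent, and ends it early when other anticancer treatment starts. Section 5.2 withdraws patients who are lost to follow-up.
- **Escalation.** Section 6.7.3: "Patients will be enrolled in cohorts of 3 beginning at dose level 1". After no DLT in three patients, Table 3 says: "Enroll 3 patients at the next dose level". It does not say when the count is taken. Section 14.1 has the team discuss further enrolment at least monthly, without a completion condition.
- **Accrual.** Section 13.2 expects 29-35 patients at 1-2 per month, and concludes that "the anticipated enrollment period is expected to be about 15-35 months".

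**The concern.** The DLT count is the primary analysis of this trial: every escalation step and the MTD depend on it. A patient should count as DLT-free only if the whole DLT window was seen. The written rule lets a patient qualify with 7 days of the window left, or 14 if the cycle is extended after 21 pazopanib doses are already in. A patient who then leaves observation is kept in the denominator with a DLT status that is partly unknown, and the error always runs towards fewer DLTs.

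The second part is timing. If a cohort decision were taken before the last patient had finished cycle 1, a late DLT could appear after the next level had opened. If the team waits, as it probably would, the enrolment estimate should contain that time.

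**Working it through.** **1. Earliest day of evaluability.** Pazopanib is daily, so dose 21 falls on day 21. On a Monday/Wednesday/Friday schedule starting on day 1, AR-42 falls on days 1, 3, 5, 8, 10, 12, so dose 6 is on day 12. Both minimums are met on day 21. Window still open: 28 - 21 = 7 days (7/28 = 25%), or 35 - 21 = 14 days (14/35 = 40%) in an extended cycle. The 14-day case can arise when only AR-42 is interrupted, because Section 7.4 generally keeps pazopanib going.

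**2. What one early leaver can hide.** Assume a constant hazard over the window and a true cycle-1 DLT risk p. For a patient free of DLT at day 21, the chance of a DLT in days 22-28 is 1 - (1 - p)^0.25:
- p = 20%: 5%
- p = 33%: 10%
- p = 40%: 12%
- p = 50%: 16%

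For the 35-day case at p = 33% it is 1 - 0.67^0.4 = 15%. The documents do not say how many patients would leave in this interval, so the total bias cannot be computed.

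**3. Effect on escalation if the last patient is read at day 21.** Table 3 escalates on 0 of 3, or on 1 of 3 followed by 0 of 3.
- Full windows, q = 1 - p: P(escalate) = q^3 + 3pq^2 × q^3. At p = 0.33: 0.3008 + 0.4444 × 0.3008 = 0.434. At p = 0.40: 0.216 + 0.432 × 0.216 = 0.309.
- Last patient of each three read at day 21: that patient's observed risk is b = 1 - (1 - p)^0.75. Then P(0 of 3) = q^2(1 - b), P(1 of 3) = 2pq(1 - b) + q^2 b, and P(escalate) = P(0 of 3) + P(1 of 3) × P(0 of 3).
- At p = 0.33: b = 0.259, P(0 of 3) = 0.332, P(1 of 3) = 0.444, P(escalate) = 0.332 + 0.444 × 0.332 = 0.480. With p = 1/3 exactly, 0.428 becomes 0.474.
- At p = 0.40: b = 0.318, P(0 of 3) = 0.245, P(1 of 3) = 0.442, P(escalate) = 0.354.

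The rise is 4-5 points at these rates, and 3-4 points at p = 20% (71% to 74%) and p = 50% (17% to 21%).

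**4. The plan's enrolment period, reproduced.** 18/0.8 = 22.5, rounded to 23; 23/0.8 = 28.75, rounded to 29. Adding 6 gives 29-35. Then 29/2 = 14.5, rounded to 15, and 35/1 = 35. The stated 15-35 months is patients divided by rate, with no observation time.

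**5. The same period with a 28-day wait.** Section 13.2 implies 4 × 4.5 = 18 to 5 × 4.5 = 22.5 evaluable patients in escalation, or 6 to 7.5 groups of three. One month is taken as 30.4 days.
- Fast end, even spacing of 15.2 days: each wait adds 28 - 15.2 = 12.8 days; 6 × 12.8 = 77 days = 2.5 months; 14.5 + 2.5 = 17 months.
- Fast end, patients arriving in a pause not held: 6 × 28 = 168 days = 5.5 months; 14.5 + 5.5 = 20 months.
- Slow end, even spacing of 30.4 days: the 28-day wait is absorbed, so 35 months.
- Slow end, arrivals not held: 7.5 × 28 = 210 days = 6.9 months; 35 + 6.9 = about 42 months.

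**The case against.** The strongest reply is that the plan already defines the DLT period as cycle 1, and Table 3 refers to that definition. A count of no DLTs in three patients is then naturally a count over the whole cycle. The dose minimum is an exposure filter, not a time at which observation stops. This stands: a reader might infer that the plan directs escalation on day 21, but no text says so. The missing wait is an unstated rule that is probably intended.

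A reader might also infer a much larger effect on escalation. Two routes lead there, and neither fits the documents:
- Reading all three patients at day 21 requires them to start together. At 2 per month with even spacing, when the last is on day 21 the others are on about days 36 and 51.
- Reading the last patient when the next one arrives, at about day 15, fails the plan's own rule, because at most 15 pazopanib doses can have been taken.

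At 1 per month with even spacing, no 28-day window is open when the next patient arrives.

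Section 6.13 narrows the evaluability gap. A patient who stops treatment for toxicity or progression normally stays under observation past day 28. The gap is limited to consent withdrawal, loss to follow-up and new anticancer therapy.

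Later safeguards also help: a level is confirmed only with at least 6 evaluable patients, and the MTD is expanded to 12 with its own DLT limit. A higher chance of passing one step is not the same as a higher chance of a wrong MTD, which is not computed here.

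What remains is that the evaluability rule, as written, keeps partly observed patients as DLT-free even if the team always waits.

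**Conclusion.** The point holds in this limited form. The evaluability rule omits observation to the end of the DLT period, so some patients with an unknown late-cycle status would be counted as DLT-free instead of being replaced. The direction of the bias is certain. Its size depends on how many patients leave between day 21 and the end of cycle 1, which the plan does not give.

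The unstated wait between cohorts is a lesser matter. If it were not observed, the consistent scenario adds about 4-5 percentage points to the chance of escalating at true DLT rates of 33% and 40%, assuming a constant hazard over 28 days and only the last patient of each three read at day 21.

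If it is observed, the fast end of the enrolment period is too short by about 2 to 5 months. A reader might infer that the whole 15-35 month range is wrong. It is not: 17-20 months lies inside it, and the slow end moves beyond 35 only if patients arriving during a pause are not held. The sample size of 29-35, maximum 51, is unaffected.

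The absence of a waiting rule is established for the text available. Some pages were not available, but Sections 6.6, 6.7, 13 and 14, where such a rule would stand, were.

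**What to change.** 1. In Sections 6.7.1 and 13.6.1, count a patient without a DLT as evaluable only if the dose minimum is met and the patient was observed for DLT to the end of cycle 1, including any extension. Otherwise replace the patient.
2. In Table 3, state that the DLT count used for a decision is taken when every patient in the cohort has either had a DLT or completed cycle 1.
3. In Sections 13.2 and 3.1, restate the enrolment period with the observation time and its assumptions: about 17-20 months at the fast end and 35 to about 42 at the slow end, the upper values applying only if patients arriving during a pause are not held.

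The cost is two sentences and one planning figure. For a patient who continues, the cycle 2 day 1 visit already includes an adverse event assessment. The downside is an occasional extra replacement, which the 20% allowance for inevaluable patients covers in part, and a somewhat longer stated enrolment period.
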